3.3.8.2 Concomitant Medications and Therapies

At each study visit, study site staff must question the participant regarding any medications taken and vaccinations received by the participant and record the following information in the eCRF:

- All non-study vaccinations administered within the period starting 28 days before the first study injection.
- All concomitant medications and non-study vaccinations taken through 28 days after each injection. Antipyretics and analgesics taken prophylactically (ie, taken in the absence of any symptoms in anticipation of an injection reaction) will be recorded as such.
- Any concomitant medications relevant to or for the treatment of an SAE or a MAAE.
- Participant will be asked in the eDiary if they have taken any antipyretic or analgesic to treat or prevent fever or pain within 7 days after each study injection, including the day of injection. Reported antipyretic or analgesic medications should be recorded in the source document by the site staff during the post-injection study visits or via other participant interactions (eg, telephone calls).

The use of the following concomitant medications and/or vaccines will not require withdrawal of the participant from the study but may determine a participant's eligibility to receive a second dose or evaluability in the per-protocol analysis (analysis sets are described in [Section 4.4](#)):

- Any investigational or nonregistered product (drug or vaccine) other than the study vaccine used during the study period.
- Immunosuppressants or other immune-modifying drugs administered chronically (ie, more than 14 days in total) during the study period. For corticosteroids, this will mean that prednisone \geq 20 mg/day or the equivalent is not permitted. Inhaled, nasal, and topical steroids are allowed.
- Long-acting immune-modifying drugs administered at any time during the study period (eg, infliximab).
- A licensed vaccine administered during the period from 28 days before through 28 days after each study injection, except for any licensed influenza vaccine that was administered more than 14 days before or after any study injection.
- Immunoglobulins and/or any blood products administered during the study period.

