4.4.5 Per-Protocol Set

The Per-Protocol (PP) Set consists of all FAS participants who meet all of the following criteria:

- Complied with the injection schedule
- Complied with the timings of immunogenicity blood sampling to have post-injection results available for at least one assay component corresponding to the immunogenicity analysis objective
- Did not have SARS-CoV-2 infection
- Have had no major protocol deviations that impact immune response during the period corresponding to the immunogenicity analysis objective

The PP Set will serve as the primary population for the analysis of immunogenicity data in Part A, Part B, and Part C of this study. Participants will be included in the treatment group to which they were randomly assigned.

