12. Trained site personnel will call all participants to collect information relating to any AEs, MAAEs, SAEs, AEs leading to study withdrawal, information on concomitant medications associated with those events, and any non-study vaccinations. In addition, study personnel will collect information on known participant exposure to someone with known COVID-19 or SARS-CoV-2 infection and on participant experience of COVID-19 symptoms. Sites will collect this information for diary days only if diary responses indicate the need for follow-up via telephone.
13. All concomitant medications and non-study vaccinations will be recorded through 28 days after each injection; all concomitant medications relevant to or for the treatment of an SAE or MAAE will be recorded from Day 1 through the final visit (Day 394).

Table 10: Part B: Participant Decision Clinic Visit

	All Participants
Return to clinic for Participant Decision Clinic Visit	X
Sign revised Informed Consent Form	X
Confirm participant's choice to be unblinded or not to be unblinded	X
Confirm participant's choice to receive open-label mRNA-1273	X
Nasopharyngeal swab	X
Blood for immunologic analysis	X
Counsel about social distancing practices ¹	X
Participant Status at end of Participant Decision Clinic Visit	Part B Schedule of Events
Consents to unblinding and to receiving either 2 doses of mRNA-1273, 28 days apart, or a single booster of mRNA-1273 (50 µg) at OL-D1 in Part B	
Received placebo in Part A	Table 11
Received 1 dose of mRNA-1273 in Part A	Table 12
Received 2 doses of mRNA-1273 in Part A	Table 12
Consents to unblinding but declines to receiving either 2 doses of mRNA-1273, 28 days apart, or a single booster of mRNA-1273 (50 µg) in Part B	
Received 1 or 2 doses of placebo in Part A	Table 12
Received 1 dose of mRNA-1273 in Part A ²	Table 12
Received 2 doses of mRNA-1273 in Part A	Table 12
Declines unblinding and mRNA-1273 or booster in Part B	Table 12

1. All participants are counselled about the importance of continuing other public health measures to limit the spread of disease including physical-social distancing, wearing a mask, and hand-washing.
2. Applies to participants in Part A who received 50 µg or 100 µg mRNA-1273.

Table 11: Part B: Open-label Schedule of Events: ONLY for Participants Receiving 2 Doses of mRNA-1273 28 Days Apart

Visit Number	0	OL-1	OL-2	OL-3	OL-4		OL-5			OL-6
Type of Visit	C	C	C	C	C	SC	C	SFU		C
Month Timepoint		OL-M0			OL-M1		OL-M2	eDiary	SC	OL-M7

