7. Diary entries will be recorded by the participant starting approximately 30 minutes after injection while at the study site with instruction provided by study staff. Study participants will continue to record in the eDiary each day after they leave the study site, preferably in the evening and at the same time each day, on the day of injection and for 6 days following injection. Any solicited AR that is ongoing beyond Day 7 will be reported in the eDiary until resolution. Adverse reactions recorded in eDiaries beyond Day 7 should be reviewed either during the next telephone call or at the next study site visit.
8. Trained site personnel will call all participants to collect information relating to any AEs, MAAEs, SAEs, AEs leading to study withdrawal, information on concomitant medications associated with those events, and any non-study vaccinations. In addition, study personnel will collect information on known participant exposure to someone with known COVID-19 or SARS-CoV-2 infection and on participant experience of COVID-19 symptoms. Sites will collect this information for diary days only if diary responses indicate the need for follow-up via telephone.
9. All concomitant medications and non-study vaccinations will be recorded through 28 days injection; all concomitant medications relevant to or for the treatment of an SAE or MAAE will be recorded from OL-Day 1 through the final visit (OL-Day 181).

NOTE: The following participants will complete the described assessments in this SOE at OL-Day 1, and will skip OL-D8, OL-D15, OL-Day 29, and OL-D57:

- Participants who received 1 or 2 doses of mRNA-1273 in Part A and decline receiving booster mRNA-1273 in Part B.
- Participants who decline unblinding
- Participants who received placebo in Part A, but decline to receive 2 doses of mRNA-1273 in Part B

Participants who decline receiving booster mRNA-1273, decline unblinding, or decline to receive 2 doses of mRNA-1273 in Part B will not receive study vaccination at OL-D1 (or OL-D29), will not perform a pregnancy test, or eDiary activation at OL-D1.

10. Blood sample for serology will be collected only at the Participant Decision Visit (OL-D1).
11. In Part C, an additional booster dose may be added approximately 56 days after the first boost at OL-D1. This additional booster dose will be triggered following review of immunogenicity data up to OL-D15 of the initial mRNA1273.351 (20 μg and 50 μg) and mRNA-1273/mRNA-1273.351 mixture injections.

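### Routine recording of outside products ends 28 days after injection, but some of them can affect per-protocol evaluability throughout the study, so affected 6-month titres may go undetected

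*Protocol*

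**What the plan says.** **Recording.** Table 9 footnote 13 (Part A) states: "All concomitant medications and non-study vaccinations will be recorded through 28 days after each injection". Table 11 footnote 8 and Table 12 footnote 9 give the same limit with words missing ("All concomitant medications and non-study vaccinations will be recorded through 28 days injection"). The second bullet of Protocol Section 3.3.8.2 agrees: "All concomitant medications and non-study vaccinations taken through 28 days after each injection". Beyond that point, the footnotes and Section 3.3.8.2 require only medications relevant to an SAE or MAAE. The first bullet of the same section gives a start but no end for vaccinations: "All non-study vaccinations administered within the period starting 28 days before the first study injection".

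**Evaluability.** Section 3.3.8.2 then lists products whose use may bear on "eligibility to receive a second dose or evaluability in the per-protocol analysis". Four classes run over the whole study period:

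- "Any investigational or nonregistered product (drug or vaccine) other than the study vaccine used during the study period"
- chronic immune-modifying drugs
- long-acting immune-modifying drugs
- "Immunoglobulins and/or any blood products administered during the study period"

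Licensed vaccines are treated differently. Their criterion covers 28 days either side of each injection, with an exception for influenza vaccine.

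**Analysis set.** Protocol Section 4.4.5 requires per-protocol participants to satisfy this condition: "Have had no major protocol deviations that impact immune response during the period corresponding to the immunogenicity analysis objective". SAP Section 5.6 (Part B, criterion d) and Part C SAP Section 5.5 (b) carry it forward.

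**Endpoints.** Late titres are primary: binding antibody at Day 209 and Day 394 in Part A, binding antibody at OL-Day 181 or OL-Day 209 in Part B, and neutralising antibody at OL-Day 181 in Part C.

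**The concern.** An exclusion can only be applied to exposures that reach the analysis database. The protocol makes four product classes relevant to evaluability for the whole study, then requires routine collection only to day 28. An immune-modifying drug could lower a later titre, and an antibody product or outside COVID-19 vaccine could raise it. If that exposure is not captured, the titre stays in the primary immunogenicity set and the persistence estimate absorbs it.

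COVID-19 vaccines matter here because Part B was prompted by their emergency authorisation and participants are told about them. Section 3.3.8.2 does not say whether such a vaccine counts as nonregistered or licensed. If nonregistered, the criterion runs over the study period while the footnotes end recording at day 28. If licensed, a dose taken more than 28 days after a study injection is not a listed ground for non-evaluability at all.

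**Working it through.** The plan gives no figure on this point to reproduce, so the check compares windows and then illustrates size.

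**1. Where the recording rows end** (Tables 9, 11 and 12, row for concomitant medications and non-study vaccinations)

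- Part A: Day 57, which is 28 days after dose 2 on Day 29.
- Part B, two doses: OL-D57, which is 28 days after dose 2 on OL-D29.
- Single booster, Parts B and C: OL-D29, 28 days after OL-D1. The marks at OL-D57 and OL-D64 carry footnote 12, which concerns the optional additional booster.

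**2. Time outside routine recording before each late titre**

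- Single booster to OL-D181: 181 - 1 = 180 days since injection; 180 - 28 = 152; 152/180 = 84%.
- Two-dose Part B to OL-D209: 209 - 29 = 180 days since dose 2; 180 - 28 = 152; 84%.
- Part A to Day 209: 209 - 29 = 180; 180 - 28 = 152; 84%.
- Part A to Day 394: 394 - 29 = 365; 365 - 28 = 337; 337/365 = 92%.

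**3. What else collects information in that stretch**

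- Safety calls under Table 12 run every 4 weeks from OL-D85 to OL-D169: OL-D85, 113, 141 and 169. They ask about any non-study vaccination, but about medications only when linked to an event. Section 3.4.3 sends call information to source documents and does not mention the eCRF.
- The eDiary questionnaire (Section 3.4.2) lists neither medications nor vaccinations.
- Section 3.4.8.7 has staff ask at every visit or call about new or changed medications and non-study vaccinations. No schedule row carries the answer into the eCRF after day 28.

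So vaccinations are asked about, with conflicting instructions on recording. Immune-modifying drugs and immunoglobulins with no linked event are covered only by the general question.

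**4. Illustrative size.** If a share f of the analysed participants has its titre multiplied by F, the mean log titre moves by f × log F, so the GMT is multiplied by F^f. Neither f nor F is in the documents; both are assumptions.

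| f | F = 0.25 | F = 2 | F = 10 |
|---|---|---|---|
| 1% | 0.986 | 1.007 | 1.023 |
| 5% | 0.933 | 1.035 | 1.122 |
| 10% | 0.871 | 1.072 | 1.259 |

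A Part C arm has 20 participants, so one participant is f = 1/20 = 5%. A 10-fold rise gives 10^0.05 = 1.122 (+12%); a 10-fold fall gives 10^-0.05 = 0.891 (-11%). In a group of 100 (one age cohort and dose level as randomised), one participant is f = 1%, and a 10-fold rise gives 1.023 (+2%).

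**5. Would the FAS comparison reveal it?** No. Supportive FAS analysis is triggered when FAS and Per-Protocol counts differ by more than 10% (SAP Section 6.4). An undetected case is in both sets and does not move that difference.

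**The case against.** The strongest reply is that collection does not stop at day 28. Vaccinations are asked about on calls and at visits, and the first bullet of Section 3.3.8.2 has no end date. The closing paragraph of that section makes the investigator responsible for adequate eCRF detail when a prohibited therapy is taken, with no time limit. Monitors document deviations. Both SAPs define a post-treatment category for medications and list it together with non-study vaccinations. The eCRF and the major-deviation rules are not among the documents. Entry criteria exclude people who anticipate immunosuppressive treatment or plan to receive immunoglobulins or blood products, which should keep f small. Analyses are descriptive, so no test threshold is at risk.

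Much of this stands. A reader might infer that outside vaccines go uncollected after day 28, or that contaminated titres do remain in the Per-Protocol Set. The documents support neither: the calls keep asking, licensed vaccines have a 28-day criterion that matches the recording window, the listed products only *may* determine evaluability, and there are partial routes to detection.

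What does not stand is that these routes close the gap. A listing shows only what was entered. The investigator's general duty has no schedule row behind it. Call reports are directed to source documents, and the last scheduled call under Table 12 (OL-D169) precedes the OL-D181 titre.

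**Conclusion.** The mismatch is real and should be reconciled. The stated recording rule cannot reliably feed the stated per-protocol assessment for four product classes over 152 of the 180 days before the 6-month primary titre. The gap is clearest for event-free immune-modifying drugs and immunoglobulins. For vaccinations it is an inconsistency between the footnotes, the open-ended bullet in Section 3.3.8.2 and the call script, with no stated route from call report to eCRF.

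The consequence is that affected late titres may go undetected. That they do, or that persistence is biased in a known direction, is not established. The +12% or -11% for one of 20 in a Part C arm rests wholly on the assumed 10-fold change; in larger groups a single case has far less effect.

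**What to change.** - **Protocol.** In Table 11 footnote 8, Table 12 footnote 9 and the second bullet of Section 3.3.8.2, keep the 28-day limit for other medications. Require non-study vaccinations (including any COVID-19 vaccine) and the study-period products listed in Section 3.3.8.2 to be entered in the eCRF, with dates, through the final visit. Extend the matching rows to the later calls and visits, add the listed drug classes to the call script, and state that call-reported vaccinations are transcribed to the eCRF.
- **SAPs.** In SAP Section 5.6 (Part B, criterion d) and Part C SAP Section 5.5 (b), state that late titres are assessed for per-protocol exclusion after an outside COVID-19 vaccine or a listed study-period product. Limit it to those: removing titres after every non-study vaccination would discard data following licensed vaccines that Section 3.3.8.2 permits.
- **Part A.** SAP Section 1 says Part A is complete and reported, so changing Table 9 footnote 13 would achieve nothing now. Review source records for such exposures before the Day 209 and Day 394 titres, or state the limitation.

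The cost is one script item, one eCRF line and some SAP wording, with slightly fewer late per-protocol titres.

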7.2 Appendix 2: Toxicity Grading Scale Tables

The toxicity grading scales for clinical and laboratory abnormalities are presented in [Table 13](#) and [Table 14](#), respectively. Note that for laboratory abnormalities, grading only occurs if the values are outside of the normal values established by the clinical laboratory. For study-specific laboratory normal ranges and associated toxicity grades, refer to the laboratory manual and provided toxicity grade communications.

Table 13: Tables for Clinical Abnormalities

Local Reaction to Injectable Product	Mild (Grade 1)	Moderate (Grade 2)	Severe (Grade 3)	Potentially Life-threatening (Grade 4)
Pain	Does not interfere with activity	Repeated use of non-narcotic pain reliever > 24 hours or interferes with activity	Any use of narcotic pain reliever or prevents daily activity	ER visit or hospitalization
Tenderness	Mild discomfort to touch	Discomfort with movement	Significant discomfort at rest	ER visit or hospitalization
Erythema/Redness *	2.5 – 5 cm	5.1 – 10 cm	> 10 cm	Necrosis or exfoliative dermatitis
Induration/Swelling **	2.5 – 5 cm and does not interfere with activity	5.1 – 10 cm or interferes with activity	> 10 cm or prevents daily activity	Necrosis

Abbreviation: ER = emergency room.

* In addition to grading the measured local reaction at the greatest single diameter, the measurement should be recorded as a continuous variable.

** Induration/swelling should be evaluated and graded using the functional scale as well as the actual measurement.

Source: Guidance for industry – Toxicity Grading Scale for Healthy Adult and Adolescent Volunteers Enrolled in Preventive Vaccine Clinical Trials; tables for clinical abnormalities ([DHHS 2007](#)).

Vital Signs *	Mild (Grade 1)	Moderate (Grade 2)	Severe (Grade 3)	Potentially Life-threatening (Grade 4)
Tachycardia (beats per minute)	101 – 115	116 – 130	> 130	ER visit or hospitalization for arrhythmia
Bradycardia (beats per minute)**	50 – 54	45 – 49	< 45	ER visit or hospitalization for arrhythmia
Hypertension (systolic) (mm Hg)	141 – 150	151 – 155	> 155	ER visit or hospitalization for malignant hypertension
Hypertension (diastolic) (mm Hg)	91 – 95	96 – 100	> 100	ER visit or hospitalization for malignant hypertension
Hypotension (systolic) (mm Hg)	85 – 89	80 – 84	< 80	ER visit or hospitalization for hypotensive shock
Respiratory rate (breaths per minute)	17 – 20	21 – 25	> 25	Intubation

Abbreviation: ER = emergency room.

Note that fever is classified under systemic reactions for grading purposes.

* Participant should be at rest for all vital sign measurements.

** When resting heart rate is between 60 – 100 beats per minute. Use clinical judgment when characterizing bradycardia among some healthy participant populations, for example, conditioned athletes.

Source: Guidance for industry – Toxicity Grading Scale for Healthy Adult and Adolescent Volunteers Enrolled in Preventive Vaccine Clinical Trials; tables for clinical abnormalities (DHHS 2007).

Systemic (General)	Mild (Grade 1)	Moderate (Grade 2)	Severe (Grade 3)	Potentially Life-threatening (Grade 4)
Fever (°C) * (°F) *	38.0 – 38.4 100.4 – 101.1	38.5 – 38.9 101.2 – 102.0	39.0 – 40.0 102.1 – 104.0	> 40.0 > 104.0
Nausea/vomiting	No interference with activity or 1 to 2 episodes/24 hours	Some interference with activity or > 2 episodes/24 hours	Prevents daily activity, requires outpatient IV hydration	ER visit or hospitalization for hypotensive shock
Diarrhea	2 – 3 loose stools or < 400 g/24 hours	4 – 5 stools or 400 – 800 g/24 hours	6 or more watery stools or > 800 g/24 hours or requires outpatient IV hydration	ER visit or hospitalization
Headache	No interference with activity	Repeated use of non-narcotic pain reliever > 24 hours or some interference with activity	Significant; any use of narcotic pain reliever or prevents daily activity	ER visit or hospitalization
Fatigue/malaise (unusual tiredness)	No interference with activity	Some interference with activity	Significant; prevents daily activity	ER visit or hospitalization
Generalized myalgia (muscle ache or pain)	No interference with activity	Some interference with activity	Significant; prevents daily activity	ER visit or hospitalization
Generalized arthralgia (joint ache or pain)	No interference with activity	Some interference with activity not requiring medical intervention	Prevents daily activity and requires medical intervention	ER visit or hospitalization

Abbreviations: ER = emergency room; IV = intravenous.

* Oral temperature; no recent hot or cold beverages or smoking.

Sources: Guidance for industry – Toxicity Grading Scale for Healthy Adult and Adolescent Volunteers Enrolled in Preventive Vaccine Clinical Trials; tables for clinical abnormalities ([DHHS 2007](#)). Division of AIDS Grading the Severity of Adult and Pediatric Adverse Events ([DHHS 2014](#)).

Table 14: Tables for Laboratory Abnormalities

Serum Chemistry*	Mild (Grade 1)	Moderate (Grade 2)	Severe (Grade 3)	Potentially Life-threatening (Grade 4)**
BUN (mg/dL)	23 – 26	27 – 31	> 31	Requires dialysis
Creatinine (mg/dL)	1.5 – 1.7	1.8 – 2.0	2.1 – 2.5	> 2.5 or requires dialysis
ALP; increase by factor	1.1 – 2.0 × ULN	2.1 – 3.0 × ULN	3.1 – 10 × ULN	> 10 × ULN
Liver function tests – ALT and AST; increase by factor	1.1 – 2.5 × ULN	2.6 – 5.0 × ULN	5.1 – 10 × ULN	> 10 × ULN
Bilirubin – when accompanied by any increase in liver function test; increase by factor	1.1 – 1.25 × ULN	1.26 – 1.5 × ULN	1.51 – 1.75 × ULN	> 1.75 × ULN
Bilirubin – when liver function test is normal; increase by factor	1.1 – 1.5 × ULN	1.6 – 2.0 × ULN	2.0 – 3.0 × ULN	> 3.0 × ULN

Abbreviations: ALP = alkaline phosphatase; ALT = alanine aminotransferase; AST = aspartate aminotransferase; BUN = blood urea nitrogen; ULN = upper limit of the normal range.

* The laboratory values provided in the tables serve as guidelines and are dependent upon institutional normal parameters. Institutional normal reference ranges should be provided to demonstrate that they are appropriate.

** The clinical signs or symptoms associated with laboratory abnormalities might result in characterization of the laboratory abnormalities as potentially life-threatening (Grade 4). For example, a low sodium value that falls within a Grade 3 parameter (125 – 129 mEq/L) should be recorded as a Grade 4 hyponatremia event if the participant had a new seizure associated with the low sodium value.

Source: Guidance for industry – Toxicity Grading Scale for Healthy Adult and Adolescent Volunteers Enrolled in Preventive Vaccine Clinical Trials; tables for laboratory abnormalities ([DHHS 2007](#)).

Hematology *	Mild (Grade 1)	Moderate (Grade 2)	Severe (Grade 3)	Potentially Life-Threatening (Grade 4)
Hemoglobin (female) (g/dL)	11.0 – 12.0	9.5 – 10.9	8.0 – 9.4	< 8.0
Hemoglobin (female) change from baseline value (g/dL)	Any decrease – 1.5	1.6 – 2.0	2.1 – 5.0	> 5.0
Hemoglobin (male) (g/dL)	12.5 – 13.5	10.5 – 12.4	8.5 – 10.4	< 8.5
Hemoglobin (male) change from baseline value (g/dL)	Any decrease – 1.5	1.6 – 2.0	2.1 – 5.0	> 5.0
WBC increase (cell/mm ³)	10,800 – 15,000	15,001 – 20,000	20,001 – 25,000	> 25,000
WBC decrease (cell/mm ³)	2,500 – 3,500	1,500 – 2,499	1,000 – 1,499	< 1,000
Lymphocytes decrease (cell/mm ³)	750 – 1,000	500 – 749	250 – 499	< 250
Neutrophils decrease (cell/mm ³)	1,500 – 2,000	1,000 – 1,499	500 – 999	< 500
Eosinophils (cell/mm ³)	650 – 1,500	1,501 – 5,000	> 5,000	Hypereosinophilic
Platelets decreased (cell/mm ³)	125,000 – 140,000	100,000 – 124,000	25,000 – 99,000	< 25,000
PT; increase by factor	> 1.0 – 1.10 × ULN	1.11 – 1.20 × ULN	1.21 – 1.25 × ULN	> 1.25 × ULN
PTT; increase by factor	> 1.0 – 1.2 × ULN	1.21 – 1.4 × ULN	1.41 – 1.5 × ULN	> 1.5 × ULN

Abbreviations: PT = prothrombin time; PTT = partial thromboplastin time; ULN = upper limit of normal; WBC = white blood cell.

* The laboratory values provided in the tables serve as guidelines and are dependent upon institutional normal parameters. Institutional normal reference ranges should be provided to demonstrate that they are appropriate. Laboratory abnormality grading occurs only when the values fall beyond the normal ranges established by the local laboratory.

Source: Guidance for industry – Toxicity Grading Scale for Healthy Adult and Adolescent Volunteers Enrolled in Preventive Vaccine Clinical Trials; tables for laboratory abnormalities (DHHS 2007). Note that the criteria for Grade 1 PT and PTT have been adjusted from the source table: instead of $\geq 1.0 \times$ ULN, both criteria are $> 1.0 \times$ ULN. Grade 1 will not be used for hematology values due to the large overlap with normal values at the central laboratory.

